1.2.1. Glucocorticoid Treatment

At present, treatment with glucocorticoid (GC) medication is the only pharmacological intervention that has been shown to slow the decline of strength and function in DMD patients. The two main GCs used in DMD are prednisone and deflazacort (EMFLAZATM). Daily oral administration of prednisone or deflazacort stabilizes or improves strength and prolongs ambulation (6-11). The mechanism by which GCs are beneficial in dystrophin deficiency is likely multifactorial, including anti-inflammatory actions. The immunosuppressive effects of GCs may not be beneficial, and other immunosuppressants have not shown benefit (8).

In 2005, the American Academy of Neurology issued a practice parameter regarding GC treatment in DMD and recommended that GC should be offered as treatment, despite known side effects (12). The significant side effects of GCs include cushingoid features, adverse behavioral changes, obesity, growth retardation, increased risk for bone fractures, gastritis, delayed puberty, cataracts, hypertension, glucose intolerance, susceptibility to infection, and masking of response to stress (13). On February 9, 2017, the United States Food and Drug Administration (FDA) approved EMFLAZATM to treat patients 5 years of age and older with DMD.

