1.3.5.2. Phase II Trials

NS065/NCNP01-P1/2 is a Phase I/II study of NS-065/NCNP-01 Injection being conducted in Japan. This is a multicenter, parallel-group, open-label, 24-week study. Participants receive weekly IV administration of NS-065/NCNP-01 Injection 250 mg (40 mg/kg and 80 mg/kg) over 24 weeks. The primary efficacy endpoint of this study is dystrophin protein expression as measured by Western blot, immunofluorescence staining, and RT-PCR. 16 DMD patients amenable to Exon 53 skipping, aged 5-<18 years are enrolled.

NS-065/NCNP-01-201 is a Phase II study conducted in the United States and Canada. This is a multicenter, 24-week dose finding study to assess the safety, tolerability, pharmacokinetics and pharmacodynamics of NS-065/NCNP-01 in boys with DMD. Participants receive weekly IV administration of NS-065/NCNP-01 Injection 250mg (40 mg/kg and 80 mg/kg) or Placebo for the first 4 weeks, followed by weekly IV administration of NS-065/NCNP-01 Injection 250mg (40 mg/kg and 80 mg/kg) over the remaining 20 weeks. The primary efficacy endpoint of this study is dystrophin protein expression as measured by Western blot. 16 DMD patients amenable to Exon 53 skipping, aged 4-<10 years were enrolled.

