4.2. Inclusion Criteria

1. Patient's parent or legal guardian has provided written informed consent/HIPAA authorization prior to any extension study-specific procedures and patient has provided assent appropriate for his age and developmental status.
2. Patient completed Study NS-065/NCNP-01-201 through Week 25.
3. Patient and parent/guardian are willing and able to comply with scheduled visits, investigational product administration plan, and study procedures.
4. Patient must be on a stable dose of GC and is expected to remain on the stable dose of GC treatment for the duration of the study.

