Pharmacokinetics and Pharmacodynamics	Pharmacokinetics and Pharmacodynamics													
PK (Blood) ¹¹														
Serum PD Biomarker												X		

Notes:

1. Week 25 of Study NS-065/NCNP-01-201 will also serve as Week 25 for first dose of Study NS-065/NCNP-01-202. End of study procedures of Study NS-065/NCNP-01-201 must be completed prior to dosing in Extension Study NS-065/NCNP-01-202
2. Perform vitals at pre-dose, at the end of infusion (+10 mins) and 1 hr (+/- 5 mins)
3. Hematology: RBC, Hb, Ht, Ret, MCV, MCH, MCHC, WBC, PLT, WBC Differential Fibrinogen, aPTT, PT-INR
4. Chemistry: Na, K, Cl, Ca, IP, BUN, Serum Creatinine, Cystatin C, AST, ALT, GGT, ALP, Haptoglobin, LDH/LDH isozyme, CK, Total bilirubin (Direct/Indirect), Total protein, Albumin, Albumin to globulin ratio, Total cholesterol, Triglyceride, Blood glucose, C-reactive protein
5. Urinalysis (Random Urine): Urine glucose, Urine blood, Urine urobilinogen, Urine specific gravity, Urine osmolarity, Urinary sediment (RBC, WBC, Cast), Urine protein (benzethonium chloride method), Albumin in urine, NAG in urine, α 1-microglobulin in urine, Urine Creatinine
6. Urine Cytology is collected along with pre-dose Urinalysis. Following Protocol Amendment 9.0 approval, the assessment should be performed at the next clinic visit, then every 6 months thereafter (i.e. Visits 133, 157, 181 and 193 or Visits 145, 169, 193, 205 and 217). Urine Cytology is collected at Visit 217 for all subjects.
7. 24hr pooled Urine in Study NS-065/NCNP-01-201 only: Urine protein (benzethonium chloride method) , Albumin in urine, NAG in urine, α 1-microglobulin in urine, Urine Cr, Urine Na, Urine K, Urine Cl, Urine IP, Uric acid in urine, β 2-microglobulin in urine and PK
8. Renal Ultrasound includes imaging of kidneys, bladder and ureters. Following Protocol Amendment 9.0 approval, the assessment should be performed at the next clinic visit, then every 6 months thereafter (i.e. Visits 133, 157, 181 and 193 or Visits 145, 169, 193, 205 and 217). Renal Ultrasound is collected at Visit 217 for all subjects.
9. Cytokine: IL-6, TNF- α , MCP-1 at pre-dose and 8hr (\pm 30min) after end of infusion
10. Function and Strength: Time to Stand (TTSTAND), Time to Climb (TTCLIMB), Time to run/walk 10 meters (TTRW), Six-minute walk Test (6MWT), North Start Ambulatory Assessment (NSAA), Quantitative Muscle Testing (QMT) and Ulnar Length
11. PK sampling timepoints: pre-dose, 1hr (+/- 5 mins) and 8hr (+/- 5 mins) after the end of the infusion

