7.6. Weight and Height

Height and weight will be collected at the visits specified in Table 1. Standing height will be collected with the patient barefoot (without shoes). The participant's legs should be kept as close together as possible and the heels should be placed back as close to the wall as possible. Participant may hold on to an object to facilitate balance. If a participant is non-ambulant, the ulnar length will be used to calculate height. Ulnar length will be measured by the CE during functional assessments (see Section 7.14.7). Weight will be collected with the patient barefoot and wearing light-weight clothes. Height and weight should take approximately 2 minutes and are not associated with any risks. These measurements are routinely performed during standard clinical examinations of patients with DMD. Weight in kilograms (kg) and height in centimeters (cm) will be documented in source documents and captured in the relevant eCRF.

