7.14.7. Ulnar Length

Ulnar length will be measured by a CE at visits specified in the schedule of study assessments (Table 1). In the event that a patient becomes non-ambulant the ulnar length will be utilized to impute height.

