10.5.1 Anthropometrics, Vital Signs, Laboratory Assessments, and ECG

Anthropometrics, vital signs, hematology, chemistry, BNP, urinalysis, and ECG results will be summarized by dose level over time using descriptive statistics for continuous outcomes. Actual values and change from Screening Visit (hematology, chemistry and urinalysis) or Day 1 (anthropometrics, vital signs and ECG) from Study NS-065/NCNP-01-201 and change from Week 25 (baseline of the NS-065/NCNP-01-202 study) will be presented. Further, all lab abnormalities will be listed.

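### Height and weight are summarised only as raw values and raw change for up to 4.14 years in growing boys on glucocorticoid, so the group summary cannot tell moderate growth slowing or excess weight gain from normal growth.

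*Combined protocol and SAP*

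**What the plan says.** **Summary of growth data.** Section 10.5.1 gives descriptive statistics by dose level over time: "Actual values and change from Screening Visit (hematology, chemistry and urinalysis) or Day 1 (anthropometrics, vital signs and ECG", both from Study 201, plus change from Week 25. The supplied text names no z-score, percentile, growth velocity, BMI or age adjustment.

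**Population.** Section 1.3.5.2 on Study 201: "16 DMD patients amenable to Exon 53 skipping, aged 4-<10 years were enrolled". Section 4.2: "Patient must be on a stable dose of GC and is expected to remain on the stable dose of GC treatment". Among the side effects of glucocorticoids, section 1.2.1 lists "obesity, growth retardation, increased risk for bone fractures".

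**Height method.** Section 7.6 sets the usual measurement: "Standing height will be collected with the patient barefoot (without shoes". It then adds: "If a participant is non-ambulant, the ulnar length will be used to calculate height". Section 7.14.7 repeats this: "In the event that a patient becomes non-ambulant the ulnar length will be utilized to impute height". Ulnar length is part of the function and strength battery, which note 10 to Table 1 ends with "Quantitative Muscle Testing (QMT) and Ulnar Length".

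**Comparator.** The historical-control comparison in section 10.6.2.2 covers function and strength tests only. Height and weight are not included.

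**The concern.** Safety is one of two co-primary objectives (section 10.5), and anthropometrics are a listed safety assessment. Expected growth depends on age, and entry ages span six years. A mean change in centimetres or kilograms therefore has no yardstick in the planned table. Comparing dose levels does not supply one: there are about 16 boys, section 10.4 expects some baseline differences, and low-dose boys move to 80 mg/kg/week under Amendment 10. Required glucocorticoid has named effects on exactly these two measurements, so a moderate shift is plausible and would be useful to describe.

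Separately, a boy who loses ambulation during the study changes height method. If his later ulna-derived height is compared with his standing height at baseline, the difference mixes growth with the disagreement between methods.

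At stake is how readable one descriptive safety table is. No dose, efficacy test, significance level or sample size depends on it.

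**Working it through.** **Follow-up time.** The plan's total reproduces: 24 weeks (Study 201) + 192 weeks (Study 202) = 216 weeks. In years (weeks × 7 / 365.25):
- Day 1 to Week 217: 216 weeks = 4.14 years
- Week 25 to Week 217: 192 weeks = 3.68 years
- Week 37 to Week 217: 180 weeks = 3.45 years

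Age at Week 217 runs from 4 + 4.14 = 8.1 to just under 10 + 4.14 = 14.1 years.

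**Height.** The documents give no growth rates, so these are assumptions.
- Normal growth of 5 to 6 cm/year: 4.14 × 5 = 20.7 cm to 4.14 × 6 = 24.8 cm.
- Growth halved: 10.3 to 12.4 cm. This lies outside the normal range and would be noticed.
- A group expected to grow 6 cm/year that grows 5 (1 − 5/6 = 17% slower): reads +20.7 cm, inside the range. The shortfall is (6 − 5) × 4.14 = 4.1 cm. With an assumed height SD of 5 to 7 cm this is 4.14/7 = 0.6 to 4.14/5 = 0.8 SD.
- Sensitivity: if expected growth is taken as 2 to 6 cm/year, the range is 8.3 to 24.8 cm, and even a cut from 6 to 3 cm/year (+12.4 cm) falls inside it. The wider the expected range, the more the raw summary can hide.

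**Weight.** At an assumed 2 to 4 kg/year, normal gain is 4.14 × 2 = 8.3 kg to 4.14 × 4 = 16.6 kg. A group expected to gain 2 kg/year could carry (4 − 2) × 4.14 = 8.3 kg of excess and stay within that range.

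**Change of height method.** The documents do not give the number of boys who switch or the ulna-to-standing difference. Assume 8 boys per dose level and a difference of 2 to 5 cm.
- One boy shifts the dose-level mean by 2/8 = 0.25 to 5/8 = 0.63 cm, which is 0.25/24.8 = 1% to 0.63/20.7 = 3% of normal change.
- His own score is off by 2/6 = 0.3 to 5/5 = 1.0 year of growth.
- At the extreme, three boys switching with an 8 cm difference would shift the mean by 3 × 8/8 = 3.0 cm.

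**Data available for a same-method change.** Height and ulnar length are both scheduled at 4 visits (section 8.1.4) + 7 (8.1.6) + 4 (8.1.7) + 1 (8.2.1) = 16 visits, every 12 weeks from Week 37 to Week 217. At Week 25, Table 1 with note 10 implies an ulnar length, but section 8.1.1 does not list one. Whether Study 201 took one on Day 1 cannot be seen here.

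**The case against.** The strongest reply is that this is a presentation choice for a descriptive table. Section 10.1 leaves detail to a SAP finalised before database lock, and no separate SAP text is supplied. The synopsis says all safety data will be listed, section 9.5.1 makes clinically significant changes adverse events, and the DSMB receives the safety data every six months and can ask for other formats. Age is summarised by dose level (section 10.4). Growth is neither a toxicology finding in section 1.3.4 nor an adverse event of special interest in section 9.5.3. With no concurrent control and glucocorticoid throughout, falling z-scores would be expected whether or not the drug affects growth.

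Much of this stands. It caps the importance, and it rules out saying that a growth problem would go unseen: a marked individual case has several routes to detection. It does not rescue the group summary. A mean baseline age does not give the expected change for boys whose ages span six years, and nothing supplied commits the SAP to an age-adjusted measure.

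A reader might also infer that the plan prescribes subtracting a standing baseline from an ulna-derived height. It does not. That follows only from reading sections 7.6, 7.14.7 and 10.5.1 together; none says which height series feeds the change score. The gap is a missing same-method rule.

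**Conclusion.** The point holds as a suggestion for improvement. As planned, the group summary of height and weight cannot distinguish moderate growth slowing or excess weight gain from normal growth over up to 4.14 years from Day 1 (3.68 from Week 25). The illustrative sizes, a 4.1 cm height shortfall and up to 8.3 kg of excess weight, rest entirely on assumed growth and weight rates. The structural point, that raw change has no age reference, does not.

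The height-method issue is secondary. It mainly distorts the switching boy's own change score and hardly moves the group mean, unless several boys switch and the two methods differ widely.

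Two stronger readings are not supported. The documents do not show that the drug affects growth, and an age-standardised deficit could not be attributed to it. Nor does either point affect dosing or any efficacy result.

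**What to change.** In section 10.5.1 or the SAP:

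1. Add z-scores for age for height, weight and BMI against one growth reference named in advance. Summarise them by visit, with change from Study 201 Day 1 and from Week 25. Label them a descriptive supplement that attributes no deficit to the drug.
2. For a boy who becomes non-ambulant, compute height change and its z-score from ulna-derived height at both time points, starting at the earliest visit with an ulnar length (Week 25 if taken, otherwise Week 37). Report no mixed-method change from Day 1 unless a Day 1 ulnar length exists. Flag ulna-derived heights in the listings.

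The cost is SAP wording and derived variables; no new measurements are needed. Each boy's own standing-to-ulna difference can be read from visits while he still walks. The downsides are that a reference must be chosen, that z-scores do not separate drug from glucocorticoid or disease, and that the ulna-based change may cover only 192 weeks, or 180 weeks from Week 37, and not reach Day 1.

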3. INVESTIGATIONAL PLAN

3.1. Overall Study Design and Plan

This is a Phase II, open-label, extension study to assess the safety and efficacy of NS-065/NCNP-01 Injection in boys with DMD after completing the 24-week dose-finding study NS-065/NCNP-01-201.

Patients must complete all study assessments of the Week 25 of Study NS-065/NCNP-01-201 before performing any study assessments in this extension study. In this extension study (NS-065/NCNP-01-202) patients will continue to receive weekly study drug infusions at the dose level up to 80 mg/kg/week for up to 192 weeks (up to a total of 216 weeks of treatment in Study NS-065/NCNP-01-201 and 202) or enrollment in a separate long-term follow up program of NS-065/NCNP-01, whichever is earlier. Once sites receive IRB approval of Protocol Amendment 10, all subjects who were previously in the low dose cohort of 40 mg/kg/week will receive 80 mg/kg/week after obtaining patient consent/assent. Week 193 is a comprehensive assessment at the beginning of the extension visits incorporated in protocol amendment 10, and Week 217 is the final study assessment for the treatment period ending with Week 216. If the site is selected to participate in the separate long-term follow-up program and the patient agrees to participate by signing the consent form before the final study visit for the NS-065/NCNP-01-202 study, then the patient should complete the Early Termination visit and transition to the new study. The decision to transition to the follow up program will be made jointly by the patient/caregiver and investigator.

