8.1.1. Day of First Infusion (Week 25)

The Week 25 study visit of Study NS-065/NCNP-01-201 shall also serve as the Week 25 dose visit if the patient wishes to continue into Extension Study NS-065/NCNP-01-202. In order to accommodate patient recovery following the scheduled biopsy during the Week 25 of Study NS-065/NCNP-01-201, patients will be allowed a visit window of 7 days (+/- 3 days) from the Week 24 infusion to complete both the end of study procedures and the first infusion in the extension study. All Week 25 study assessments of the NS-065/NCNP-01-201 study, including muscle biopsy, must be completed prior to first infusion in this extension study. Patients can receive the first infusion of this extension study on the same day as the Week 25 study visit of NS-065/NCNP-01-201, as long as all study assessments (including muscle biopsy) of NS-065/NCNP-01-201 are completed prior to infusion. Initial and Week 25 study assessments of NS-065/NCNP-01-201 will be used as baseline values for this extension study.

At Week 25 of Extension Study NS-065/NCNP-01-202, the following activities will occur:

- Inclusion/Exclusion Confirmation and Review
- Review of Medical, Surgical, Medication, and Treatment History (confirmation of concomitant medications and other treatments; any changes will be noted)*
- AE Review*
- Vital signs
- Blood draw for BNP (note this assessment may be collected with the other laboratory assessment draws for week 25 as part of Study NS-065/NCNP-01-201)
- Investigational product administration

*If Week 25 of the Extension Study occurs on the same day as Week 25 of NS-065/NCNP-01-201, these assessments do not need to be repeated.

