10. PLANNED STATISTICAL METHODS

10.1 General Considerations

The statistical analyses described in this section will be performed as further outlined in the Statistical Analysis Plan (SAP), which will be finalized prior to database lock. The SAP will supersede the protocol if there are any differences between the two documents in the plans for data analysis and the differences will be noted in the SAP. The SAP will be included as an appendix in the clinical study report for this protocol. Statistical analyses will be performed using SAS 9.4 or higher.

Patients will be enrolled in this study after completing Study NS-065/NCNP-01-201 and will continue with the study dose (40 mg/kg/week or 80 mg/kg/week) they received in Study NS-065/NCNP-01-201. Results for this study will be summarized by study dose.

Statistical analyses will occur at the following times:

- Every 6 months. A report for the DSMB will be produced including all safety data available at the temporary data lock. A template report will be provided to the DSMB prior to the first report, and the report formats will be updated at the DSMB's requests as the data develop. The DSMB will review completeness of efficacy data, but will not review the efficacy data itself.
- At the conclusion of the study. A summary report will be generated on all baseline characteristics, safety assessments and efficacy assessments, addressing each of the primary, secondary and exploratory objectives of the study.

All statistical tests will be performed at a two-sided significance level of 0.05 with no corrections for multiple comparisons or multiple outcomes. Note however, that since this is an early phase extension study, with a focus on safety, the emphasis will not be on statistical tests (i.e., p-values).

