10.3 Analysis Populations

All analyses will be based on the actual treatment each patient received. Two populations will be defined for data analysis: the Safety Population and the Full Analysis Set.

Safety Population

All patients who receive at least one dose of NS-065/NCNP-01 Injection 250 mg in both the dose-finding (NS-065/NCNP-01-201) and extension study (NS-065/NCNP-01-202) will be included in the Safety Population. The Safety Population is the primary analysis population for safety assessments.

Full Analysis Set (FAS)

All patients who receive at least one dose of NS-065/NCNP-01 Injection 250 mg in both the dose-finding (NS-065/NCNP-01-201) and extension study (NS-065/NCNP-01-202) will be included in the FAS. The FAS is the primary analysis population for clinical efficacy and exploratory PD assessments.

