10.4 Demographics and Baseline Characteristics

Summaries of patient demographics (age, race, ethnicity and dominant hand), baseline safety characteristics (anthropometrics, vital signs, physical examination, hematology, chemistry, BNP, urinalysis, ECG and antibodies), and baseline efficacy parameters will be done by dose level. Note that two sets of baseline values will be summarized, Screening Visit (from Dose-finding Study NS-065/NCNP-01-201) and Week 25 (from Extension Study NS-065/NCNP-01-202).

Any differences in distribution of baseline characteristics will be noted, although with such a small study, it is to be expected that some differences will emerge.

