10.5 Safety Assessments

Safety analyses will be performed using the safety population and will address one of two co-primary objectives of the study. All safety assessments will be based on actual treatments received by participants.

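### Section 10.1 still assumes a constant dose after Amendment 10, so the planned by-dose safety summaries would misdescribe the boys moved from 40 to 80 mg/kg/week

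*Combined protocol and SAP*

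**What the plan says.** Section 3.1 states that, once a site's IRB has approved Amendment 10, "all subjects who were previously in the low dose cohort of 40 mg/kg/week will receive 80 mg/kg/week after obtaining patient consent/assent". Section 5.2 and the Synopsis agree. Section 3.2.2.1 leaves the increase to the investigator after IRB approval and a signed consent form. No switch week is fixed, so dates may differ between boys.

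The statistical section describes a different design. Section 10.1 says that patients "will continue with the study dose (40 mg/kg/week or 80 mg/kg/week) they received in Study NS-065/NCNP-01-201", and then: "Results for this study will be summarized by study dose". Section 10.3 says: "All analyses will be based on the actual treatment each patient received". Section 10.5 repeats this for safety: "All safety assessments will be based on actual treatments received by participants".

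For anthropometrics, vital signs, laboratory data and ECG, Section 10.5.1 presents "Actual values and change from Screening Visit (hematology, chemistry and urinalysis) or Day 1 (anthropometrics, vital signs and ECG) from Study NS-065/NCNP-01-201", together with change from Week 25, by dose level over time. Section 8.1.1 has the same two reference points ("Initial and Week 25 study assessments of NS-065/NCNP-01-201 will be used as baseline values for this extension study"), and Section 10.4 says that "two sets of baseline values will be summarized, Screening Visit (from Dose-finding Study NS-065/NCNP-01-201) and Week 25" for the baseline tables. None of these sections defines a baseline just before the dose increase or says how a boy with both doses is classed.

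**The concern.** Safety and tolerability of the low and high doses is a primary objective (Section 2.1), and its summaries are organized by dose level. After Amendment 10, the sentence in Section 10.1 that defines those levels is no longer true for the low-dose cohort.

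If Section 10.1 is followed, values recorded at 80 mg/kg are reported under 40 mg/kg. If Sections 10.3 and 10.5 are followed, recently moved boys are pooled under 80 mg/kg with boys who had that dose throughout, and their change scores start before the switch. Those scores combine the dose step with the earlier period at 40 mg/kg, growth and disease progression. The moved boys are the only planned within-boy increase from 40 to 80 mg/kg, and neither layout describes them correctly.

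**Working it through.** The plan gives no figure to reproduce; Section 10.2 says the sample size has no statistical basis. The check compares the text and then counts weeks.

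**1. Consistency of the rules.** Sections 10.1, 10.3 and 10.5 agree only if nobody changes dose. Section 3.1 changes the dose of a whole cohort. In Appendix 3, the sections listed for the dose change are the Synopsis, 3.1, 3.2.2.1 and 5.2; nothing in Section 10 is listed for it.

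**2. Effect on the columns at Week 217.** Inputs: about 16 boys (Section 10.2); low-dose cohort size assumed; all low-dose boys assumed to move and stay.

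| Low-dose boys (assumed) | By Study 201 dose, 40 / 80 | By actual dose at visit, 40 / 80 |
|---|---|---|
| 6 | 6 / 10 | 0 / 16 |
| 8 | 8 / 8 | 0 / 16 |
| 10 | 10 / 6 | 0 / 16 |

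The same data give different tables under the two rules.

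**3. What a change score spans.** Let s be the switch week (assumed). At Week 217 the weeks at 80 mg/kg are 217 − s. The share of the interval is (217 − s)/(217 − 25) from Week 25 and (217 − s)/(217 − 1) from Day 1. Notes 6 and 8 to Table 1 place the start of the assessments added by Amendment 9 at Week 133 or 145, and Amendment 10 came later, so I take Weeks 133 to 205 as the range. Week 193 is a natural central case because Section 3.1 ties that visit to Amendment 10.

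| Switch week s | Weeks at 80 by Week 217 | Share from Week 25 | Share from Day 1 |
|---|---|---|---|
| 133 | 84 | 84/192 = 43.8% | 84/216 = 38.9% |
| 145 | 72 | 72/192 = 37.5% | 72/216 = 33.3% |
| 193 | 24 | 24/192 = 12.5% | 24/216 = 11.1% |
| 205 | 12 | 12/192 = 6.25% | 12/216 = 5.6% |

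An original high-dose boy has 192 of 192 weeks at 80 mg/kg since Week 25. With s = 193 and 8 boys in each cohort, the pooled 80 mg/kg column averages (8 × 24 + 8 × 192)/16 = 108 weeks at that dose, which describes neither group.

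**4. What a pre-switch baseline changes.** Hematology and chemistry are 12-weekly after Week 49 and are drawn before the infusion (Sections 8.1.6 and 8.1.7). For s = 193 the next panel is Week 205. Change from Week 25 covers 205 − 25 = 180 weeks, of which 12 are at 80 mg/kg (12/180 = 6.7%). Change from the pre-dose Week 193 panel covers 12 weeks, all at 80 mg/kg. If the switch falls between panels, say at Week 200, the span is still 12 weeks, but only 205 − 200 = 5 are at 80 mg/kg. The interval becomes much shorter; it is not always pure 80 mg/kg exposure.

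**5. Data available after the switch.** Laboratory panels up to Week 217 number 7, 6, 2 and 1 for switches at Weeks 133, 145, 193 and 205.

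**The case against.** There are four serious counter-arguments.

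- **Listings.** The Synopsis commits to listing all safety data, and Section 10.5.1 to listing all laboratory abnormalities. With about 8 moved boys (assumed), a reader can follow each boy across his own switch. This stands. A reader might infer that the within-boy information is lost; the documents do not support that. Only the summaries are deficient.
- **The actual-treatment rule.** Section 10.5 is the parent of 10.5.1 and is specific to safety, so it should prevail over a leftover general sentence. This largely stands, and a reader would go too far in calling the safety column wholly undefined. What remains is a false sentence in 10.1, no separation of moved boys from those at 80 mg/kg throughout, and no baseline near the switch.
- **The separate SAP.** Section 10.1 says it gives further detail, overrides the protocol and is finalized before database lock. Its text is not in the file reviewed and may already settle the matter. The gap is shown for the protocol text only.
- **Safety oversight.** Investigators review every out-of-range laboratory result (Section 9.10), urinalysis abnormalities are confirmed (9.11), renal thresholds are events of special interest (9.5.3), and the DSMB receives a report every six months (9.15). This stands: detection of harm in individual boys does not depend on the 10.5.1 means.

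**Conclusion.** The point holds as a modest correction to the reporting plan. Section 10.1 states a dosing rule that Amendment 10 made untrue, and the by-dose safety summaries would misdescribe the moved boys whichever column rule is used.

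Under the assumed switch weeks of 133 to 205, 6.25% to 43.8% of the Week 25 to Week 217 interval is at 80 mg/kg, so most of it is at 40 mg/kg throughout that range. Switch dates, cohort sizes and full uptake of the higher dose are assumptions; the documents give none of them.

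A reader might infer that the remaining 56% to 94% of a change score is an effect of time at 40 mg/kg. That does not follow. These are shares of calendar time, and the documents give no drift or variability figures. For a parameter that is stable over time, change from Week 25 could show mainly the dose step.

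**What to change.** In Sections 10.1 and 10.5.1, or in the SAP before database lock:

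1. Replace the constant-dose sentence in 10.1 with one that describes the Amendment 10 move.
2. Summarize safety data in three columns by actual dose at the visit: 40 mg/kg period, 80 mg/kg after switch, and 80 mg/kg throughout. Moved boys contribute to two columns, which a footnote should say.
3. For moved boys, add one descriptive change from the last assessment before the first 80 mg/kg infusion, shown by scheduled visit after the switch. Keep the two existing baselines. Separate time windows for each analyte are not worthwhile with so few boys.

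The cost is a small amount of programming on data already collected, with no new visit, sample or dosing rule. Late switchers will supply few post-switch values, and missed COVID-19 assessments or early transfer to the follow-up program would reduce them further. The added baseline shortens drift from growth and disease but does not remove it.
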